Investigation procedures	
Subject recruitment
 
The test subjects are recruited at the University of Physiotherapy THIM in Landquart and the University of Applied Sciences and Arts Southern Switzerland in Landquart.
 
The subject information and the declaration of consent are given to the test subjects. In the subject information there is a checklist that the test persons must fill out in order to check the inclusion and exclusion criteria.
 
If the subjects agree with the information, have completed the checklist and signed the consent, they will be summoned to make an appointment for the measurement.
 
Investigation Protocol
 
As soon as the signed consent of the test person has been received and an appointment has been made, the following procedure is followed. The anthropometric data of the subjects will be collected and group randomization will be carried out. Afterwards, the baseline measurements are carried out and the measurement of the skin temperature is started. Then the muscle soreness protocol (6 x 12 to 15 one-legged knee extensor protocol with a 2-minute break between sets) is completed. Cooling group A then receives the first 20-minute cooling of the thigh group.
 
Cooling group B and the control group leave the laboratory 20 minutes after the muscle soreness protocol. The measurement of skin temperature is stopped within all groups 20 minutes after the muscle soreness protocol.
 
Cooling group B begins cooling the thigh muscles 24 hours after the muscle soreness protocol. Both cooling groups perform cooling of the thigh muscles 3 x / day for the duration of the data collection (up to 72 hours according to the muscle soreness protocol).
 
At intervals of 24, 48 and 72 hours, the primary endpoints of the study are collected again. These include: muscle soreness, inflammation levels, muscle swelling, maximum voluntary isometric contraction of the thigh muscles.
 
Measurement of sore muscles
 
The level of ventrally felt muscle soreness symptoms is measured using a VAS scale (0 – 10 cm). The test subjects rate the perceived muscle soreness in both ventral thighs in a 90° knee flexion position. The measurement takes place during the baseline measurement and, 24 hours, 48 hours and 72 hours after the intervention.
 
Inflammation levels
 
The inflammation values (blood sedimentation rate, C-reactive protein, creatine kinase) are determined by venous blood sampling. The measurement takes place during the baseline measurement and, 24 hours, 48 hours and 72 hours after the intervention.
 
Muscle swelling
 
The measurement of muscle swelling of the quadriceps femoris muscle is carried out by ultrasound measurement. The measurement is carried out in a resting position and a cross-section of the muscle is recorded. The measurement takes place during the baseline measurement and, 24 hours, 48 hours and 72 hours after the intervention.
 
Measurement of maximum voluntary isometric thigh muscle contraction (MVIC)
 
MVIC is performed on an ergometer chair for biomechanical measurements and is given in kg. The measurement takes place during the baseline measurement and, 24 hours, 48 hours and 72 hours after the intervention.
 
Surface temperature
 
The surface temperature is measured using the iButton system. These sensors are glued to the skin for the duration of the measurement. The button sensors store the current temperature information and can then be read out via a computer. These measurements are started during the baseline survey, for the duration of the muscle soreness protocol, and up to 20 minutes after the muscle soreness protocol.
 
Detection of thermal perception
 
The thermal perception of the participants is recorded immediately after exposure to cold using the standardized Thermal Perception Scale (-4 to +4). This scale ranges from -4 ("extremely cold") to +4 ("extremely warm"), with 0 being considered neutral. The evaluation is carried out

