The subjects in group A (immediate cooling) receive the first cooling on the two thighs immediately after the end of the muscle soreness protocol. This cooling is carried out in the supine position. After this application, you can leave the laboratory and the measurement of the skin temperature is stopped.

Group B (delayed cooling) and group C (control group) do not receive any cooling (group B) or any intervention (group C) immediately after the muscle soreness protocol. However, you will also need to spend 20 minutes lying on your back in the lab before the skin temperature measurement is completed.

Follow-up measurements

Follow-up measurements will be taken for each measurement in the same order as for the baseline measurement ((1) Inflammatory markers, (2) Muscle swelling, (3) Soreness of muscles, (4) Maximum voluntary isometric contraction). The follow-up measurements take place 24, 48, and 72 hours after the muscle soreness protocol in the laboratory in Landquart.

The measurement method and the equipment used for each specific result are described in Chapter 3.2.

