4 STATISTICS AND METHODOLOGY

4.1. Statistical analysis plan and sample size calculation

Sample calculation

Before any data collection is carried out, case number planning and sample size calculation is necessary in order to obtain valid results. In clinical trials and animal experiments, this is even mandatory and is carefully reviewed before approval is granted (MDR, Annex XV, Chapter 1, Section 2.1, DIN EN ISO 14155:2021-05). Postoperative cryotherapy utilizing ice packs, cooling, or continuous cryotherapy devices reduced pain scores on the visual analogue scale and analgesic consumption in about half of the research studies comparing these outcomes against their control (no cryotherapy). The average initial VAS score after pain induction varies depending on the study and is an approximation of a baseline value of 4.73 ± 2.39 . A reduction in the VAS score after cold application was assumed to be an average of 47%. After taking into account the dropout rate of 10% and splitting into 3 randomized groups, a patient count of 15 subjects per study arm is considered statistically appropriate. The results were determined using the PASS 2023 version 23.0.1 software.

Numerical Results for Multiarm Tests for the Difference Between Treatment and Control Agents Assuming Equal Variance

Solve for:	Number of cases
Group distribution:	equal to ($N_c = N_1 = N_2 = \dots$)
Test Type:	T-Test
Hypothesis:	$H_0: \delta = 0$ vs. $H_1: \delta \neq 0$
Number of groups:	3
Bonferroni Correction:	none (divisor = 1)

Comparison	Target Strength	Real	Number of cases	Mean μ_i	Difference δ_i	Standard deviation σ	Alpha
Control			13	4,72		2,1	
vs. A	0,8	0,832 33	13	2,21	-2,51	2,1	0,05
vs. B	0,8	0,912 87	13	1,87	-2,85	2,1	0,05
Total	n/a	n/a	39	n/a	n/a	n/a	n/a

Comparison	The group involved in the comparison between the treatment and control shown in this report row. The comparison is made on the basis of the difference.
Test Strength	The desired test strength. Test strength is the probability of rejecting a false null hypothesis for this comparison. This test strength refers only to the comparison shown in this line.
Really. TS	The test strength that is really achieved.
N_i	The number of elements in the i th group. The total sample size is displayed in the last row of the column.
μ_i	The mean value of the i th group at which the test strength is calculated. The first row contains μ_c , the mean value of the control group.

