δ_i	The difference between the i th treatment agent and the control agent ($\mu_i - \mu_c$) for which the test strength is calculated.
σ	The standard deviation of the responses within each group.
Alpha	The probability of rejecting the null hypothesis that the control mean is equal to the treatment mean described in this row.

Summary statements

A parallel 3-group design (with a control group and 2 treatment groups) is used to test whether the mean for each treatment group is different from the mean of the control group ($H_0: \delta = 0$ versus $H_1: \delta \neq 0, \delta = \mu_i - \mu_c$). The hypotheses are evaluated using two two-sided, two-sample methods. Bonferroni-adjusted t-tests with the same variance and an overall (experimental) Type I error rate (α) of 0.05. The common standard deviation for all groups is assumed to be 2.1. The mean value of the control group is assumed to be 4.72. The treatment means 2.21 and 1.87 with at least 80% test strength to be detected in each case. For the test, the (same) group sample size needed for each of the three groups (control and treatments) is 13 (39 subjects in total). The group sample sizes were calculated using PASS 2023, version 23.0.1.

Sample size taking into account the dropout rate

Group	Dropouts Abandonment Rate	Number of cases/group	Number of cases with drop-out rate	Number of abandoned participants
1 - 3	10%	13	15	2
Total	n/a	39	45	6

Taking into account the drop-out rate

Taking into account a dropout rate of 10%, the group sizes in each study arm should be 15 subjects.

Statistical approach to examine the primary endpoints

The statistical analysis is performed using IBM SPSS Statistics (version 27, IBM Corp., Armonk, NY, USA) and the significance level is set to $p < 0.05$.

In order to be able to determine the differences between groups, a repeated ANOVA analysis is carried out with a factor of 1: time (baseline, 24 hours, 48 hours, 72 hours) and a factor of 2:

intervention (group A, group B, group C) for the recovery parameters (inflammation values, muscle swelling, muscle soreness data, maximum voluntary isometric muscle contraction).

The examination is discontinued if the participants are intolerant to the local cold application. Participants in the IC and DC groups are instructed to cancel a cooling session and contact their contact immediately if they experience symptoms such as severe pain/discomfort as a result of the cooling.

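### Section 4.1 treats the pre-exercise baseline as a fourth time level instead of a covariate, which loses precision for strength, swelling and blood markers, by an amount that depends on the ANOVA term read and the baseline correlation

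*Combined protocol and SAP*

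**What the plan says.** The only analysis planned for the primary endpoints is in section 4.1: "a repeated ANOVA analysis is carried out with a factor of 1: time (baseline, 24 hours, 48 hours, 72 hours"), crossed with intervention (groups A, B and C). It applies to inflammation values, swelling, soreness and maximum voluntary isometric contraction (MVIC), and "the significance level is set to $p < 0.05". No baseline covariate or baseline-adjusted difference is mentioned. Sex is considered in the lot-drawing procedure (section 3.3) and covariates are mentioned again in section 6.1, but in both places for allocation, not analysis. Section 4.1 does not say whether the group term or the group-by-time term decides.

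The Synopsis says of each primary measure: "The measurement takes place during the baseline measurement and, 24 hours, 48 hours and 72 hours after the intervention". The day plan in section 3.3 puts the baseline measurement before the exercise and before group A's first cooling. On the later visits, "Follow-up measurements will be taken for each measurement in the same order as for the baseline measurement". Every analysed subject should therefore have a pre-treatment value of every primary measure.

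The sample size is based on single comparisons of soreness: "The hypotheses are evaluated using two two-sided, two-sample methods". The Bonferroni entry is "none (divisor = 1").

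**The concern.** A value taken before treatment tells us about the person, not about cooling. Modelling it as an outcome has a different cost for each term of the ANOVA.

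- **Group term.** It averages three visits at which the arms can differ with one at which they should not. Stable differences between people, such as body size or habitual strength, remain in its error.
- **Group-by-time term.** Baseline acts as the reference, so nothing is diluted. It enters as a raw change score, however, which is the best use of it only when baseline and follow-up are very highly correlated.

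With arms this small, chance baseline differences are not trivial. The standard error of the difference between two arms is sqrt(2/13) = 0.39 SD with 13 per arm and sqrt(2/15) = 0.37 SD with 15. At stake is the chance of missing a real effect on MVIC, muscle thickness or the blood markers. Section 4.2 does not replace drop-outs, so lost precision cannot be bought back by recruiting.

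**Working it through.** **1. The plan's own figures.** "The common standard deviation for all groups is assumed to be 2.1"; "The mean value of the control group is assumed to be 4.72". The differences are 2.51 (A) and 2.85 (B), with 13 per arm and two-sided alpha 0.05. The noncentrality is (2.51/2.1)/sqrt(2/13) = 3.05 for A and (2.85/2.1)/sqrt(2/13) = 3.46 for B. On 24 degrees of freedom, power is 83.2% and 91.3%, matching the plan's 0.83233 and 0.91287. These describe a t-test at one time point, not the planned ANOVA.

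**2. Assumptions for the ANOVA.** The documents give no correlation between visits, and no SD for any endpoint except soreness. I assume 13 per arm, equal correlation rho between all visits, unit SD, and an effect of 0.8 SD in both cooled arms at 24, 48 and 72 hours. The centred group effects have sum of squares 0.8² × 2/3 = 0.4267.

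**3. Noncentrality of each test.**

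- Planned group term, F(2,36): 13 × 0.4267 × (3/4)² / [(1+3rho)/4].
- Planned group-by-time, F(6,108): 13 × 0.4267 × (3/4) / (1−rho).
- Group term on the follow-up mean with baseline as covariate, F(2,35): 13 × 0.4267 / [(1−rho)(1+3rho)/3].

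| rho | Group term | Group-by-time | Adjusted group term |
|---|---|---|---|
| 0.5 | 3.12/0.625 = 4.99 | 4.16/0.5 = 8.32 | 5.547/0.4167 = 13.31 |
| 0.7 | 3.12/0.775 = 4.03 | 4.16/0.3 = 13.87 | 5.547/0.31 = 17.89 |

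The first two add up to the third, apart from rounding. The planned model splits the information on a sustained effect between its two terms, in shares 3(1−rho)/4 and (1+3rho)/4: 37.5% and 62.5% at rho 0.5, 22.5% and 77.5% at 0.7, and 7.5% and 92.5% at 0.9.

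**4. Power for the constant effect, by simulation (range over repeated runs).**

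| rho | Group term | Group-by-time | Adjusted group term |
|---|---|---|---|
| 0.5 | 47% | 50–54% | 87–89% |
| 0.7 | 38–40% | 78% | 95% |
| 0.9 | 33% | about 100% | about 100% |

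Type I error was 4.6–5.6% for all three.

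**5. Like for like.** The table sets a 6-df interaction against a 2-df averaged contrast, so part of the gap is degrees of freedom. A 2-df change-score test with no covariate already reaches 69% at rho 0.5 and 90% at 0.7. The fair comparison is a joint multivariate test of group differences over 24, 48 and 72 hours: 47% on change scores and 68% with the covariate at rho 0.5. At rho 0.9 the change score keeps (1 + 2.7)/4 = 92.5% of the efficiency. For a smaller effect of 0.3 SD, the averaged tests there have 55% and 57% power.

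**6. Effects that vary over time.** Section 2.3 starts group B's cooling 24 hours after exercise, when the 24-hour measures are also due. The order at that visit is not stated. If B has no effect at 24 hours:

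| rho | Group term | Group-by-time | Adjusted group term |
|---|---|---|---|
| 0.5 | 37% | 77% | 76% |
| 0.7 | 32% | 97% | 90% |

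The joint test at rho 0.5 is then 75% unadjusted and 83% adjusted. With crossing time courses (A 0.8, 0.4, 0; B 0, 0.4, 0.8) at rho 0.5, the planned interaction has 91% power and the averaged adjusted group term 32%.

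**7. Soreness.** People with current pain are excluded, so soreness before exercise should be near zero. With an assumed baseline SD of 0.3, correlation 0.1 with follow-up and rho 0.5 between follow-up visits, power for A against control at a difference of 2.51 is 94.4% for the four-level group contrast and 94.9% with the covariate.

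**The case against.** The strongest reply is that the plan already contains a term that uses baseline well. Group-by-time takes each person as their own reference and, unlike an average over visits, detects differences in timing. Immediate against delayed cooling is a stated hypothesis (section 2.1), so timing matters. This stands. A reader might infer that the planned model loses power whichever term is read and whatever replaces it. Step 6 shows otherwise: against an averaged adjusted group term, the planned interaction can be equal or much better.

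The second reply is that MVIC and muscle thickness may be so stable within people that a change score is nearly optimal. This also stands if rho is about 0.9, but the documents give no value, and a change score is clearly less efficient at 0.5. It does not rescue the group term, which gets worse as rho rises.

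A third reply is that taking baseline out of the time factor removes the model's test that the exercise produced soreness, swelling and strength loss. That is fair, and the fix keeps a descriptive comparison for it.

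**Conclusion.** The concern holds in a limited form. If the group term is read, the loss is large: about 47% against 87% power at rho 0.5, and 40% against 95% at rho 0.7, for a constant 0.8 SD effect. If group-by-time is read, the like-for-like loss is moderate at rho 0.5 (47% against 68% for a constant effect, 75% against 83% if B has no effect at 24 hours) and almost nil at rho 0.9. These figures rest on an assumed rho, an assumed effect size and equal correlation between visits.

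Two stronger readings are not supported. A reader might expect the usual covariate gain for soreness, the endpoint used for sizing. With a baseline near zero there is little to gain, so the stated 83.2% and 91.3% should not be revised upwards on this account. A reader might also infer that the planned tests are biased or anti-conservative. They are not: chance imbalance under randomisation is not bias, and type I error stays near 5%. What is lost is precision, mainly for MVIC, muscle thickness and those blood markers with moderate correlation. The change is worth making because it is nearly free.

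**What to change.** In section 4.1, before analysis:

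- Define the time factor as 24, 48 and 72 hours.
- Enter each subject's own pre-exercise value of the same measure as a mean-centred covariate, for every primary measure.
- Keep group and group-by-time. Base the group question on a baseline-adjusted joint test of group differences over the three visits, and report adjusted differences with confidence intervals at each visit.
- Do not rely on the group term averaged over visits alone, because group B starts cooling only at 24 hours and effects may differ in timing.
- Keep a descriptive comparison of baseline with follow-up, to show that the exercise induced soreness, swelling and strength loss.

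The cost is a short amendment to section 4.1, one error degree of freedom per model and an assumption of a common baseline slope across groups. No new data are needed, and the SPSS software already named can fit the model. For soreness the covariate does no harm if baseline is near zero.

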2.3 Investigation design

This study is a single-center, randomized, controlled trial with 3 arms. After the subjects have been admitted to the examination, they are divided into one of the 3 groups.

Group A: immediate cooling according to the muscle soreness protocol

Group B: delayed cooling according to the muscle soreness protocol (24 hours delayed)

Group C: Control group

This examination is a clinical trial of risk category A.

Group A: immediate cooling

In this group, cooling starts immediately after the muscle soreness protocol. Cooling is carried out 3 x /day both on the day of the muscle soreness protocol and for a period of 72 hours. Both thighs are cooled with the "Cold Hot Maxi Pack" from Axanova for a period of 20 minutes.

Cooling log: Day 1 (muscle soreness log, 3x/day), Day 2 (3x/day), Day 3 (3x/day), Day 4 (3x/day)

Group B: delayed cooling

In this group, cooling starts 24 hours after the sore muscle protocol. Cooling is also carried out 3 x /day for a period of 72 hours. Both thighs are cooled with the "Cold Hot Maxi Pack" from Axanova for a period of 20 minutes.

Cooling log: Day 1 (muscle soreness log, no cooling), Day 2 (3x/day), Day 3 (3x/day), Day 4 (3x/day).

Group C: Control group

This group receives according to the muscle soreness protocol and will not receive any cooling intervention, nor any other intervention, for the entire period thereafter.

Sore muscle protocol

To induce sore muscles, the test subjects perform one-sided, 6 times 12 – 15 knee extensors on an ergometer chair. They straighten and bend the knee as far as possible. They repeated the exercise 5 more times after a 2-minute break (a total of 6 rounds). The movement sequences are observed and corrected if necessary. A similar protocol has already been successfully used in the literature to induce muscle soreness (Ruas et al 2022, Comparison between eccentric-only and coupled concentric-eccentric contractions for neuromuscular fatigue and muscle damage). In order to increase the significance of the investigation, the subjects are asked not to carry out any additional interventions during the experimental phase.

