a TANITA-TBF 611 scale (Tokyo, Japan). The estimate of the percentage of lower body fat was chosen because the cold pack was applied to the thigh, which mainly affects the lower extremities. Recovery parameters (see Exact Measurement Method and Primary and Secondary Endpoints) are assessed in the same order for each measurement: (1) Inflammation Scores, (2) Muscle Swelling, (3) Soreness, (4) Maximum Voluntary Isosomic Muscle Contraction. The measurement method and the equipment used for each specific result are described in Chapter 3.2.

Randomization

The randomization of the subjects will take place on the day of the baseline measurement by drawing a lot. It is ensured that the same number of tickets are available for each intervention group (5 tickets per group) and test subjects. If the number of subjects in a group exceeds one third of the total number of subjects, the lots of this group will be removed. In order to ensure the equality of the groups in terms of covariates and gender, the composition of the groups is monitored. As soon as half of a group consists of male or female subjects, the tickets for this group are removed for future subjects of the same sex.

The tickets are made of folded paper with the numbers 1, 2 or 3 on them and are placed together in a container. The drawing of the lots is carried out by the test persons themselves. After the draw, the subjects hand over the unread ticket to the study director, who assigns them to a group.

Blinding

Since cold applications are tested in this study, blinding is not possible.

Sore muscle protocol

To induce muscle soreness, a one-legged knee extensor protocol is used, which has already been used (Ruas et al., 2022). Participants will be instructed to straighten and bend their knee for 6 sets for 12 – 15 reps, with 2 minutes rest between sets. During the 2-minute break, the participants are allowed to sit on the chair. The execution of the knee extensor protocol is visually observed by an examiner. Verbal corrections of the execution can be given by the examiner. However, no verbal encouragement is given. All training sessions are carried out in the morning. If a participant is unable to perform all the repetitions of a set due to extreme fatigue or maximum effort, the set can be stopped and a new set can be started after the rest period. However, at least 12 repetitions per set must be performed. Otherwise, this will be considered an abandonment.

Intervention

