3.4 Withdrawal and discontinuation

Participants can withdraw from the investigation at any time and without giving reasons. Participants will be excluded from the examination if an imminent injury or illness contraindications exercise or cold application.

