4.2. Handling of missing data and drop-outs

Missing data, missed training sessions or abandonments are noted in the CRF. Data from patients who discontinue the examination is collected and stored. Drop-outs are not replaced by the recruitment of new participants. If consent is withdrawn, the data already collected will be included in the analysis for scientific and safety reasons. These are only anonymised after the analysis (Art. 32 ClinO-MD).

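### The cold-intolerance rule does not say what ends; read as ending participation, it acts after randomisation in the two cooling arms only and can tilt the soreness comparison towards cooling

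*Combined protocol and SAP*

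**What the plan says.** At the end of section 4.1, after the ANOVA description, the plan states: "The examination is discontinued if the participants are intolerant to the local cold application". The sentence that follows gives another consequence for symptoms such as severe pain or discomfort from cooling: "Participants in the IC and DC groups are instructed to cancel a cooling session and contact their contact immediately". IC and DC are evidently groups A and B.

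The order of events is fixed elsewhere. Section 3.3: "The randomization of the subjects will take place on the day of the baseline measurement by drawing a lot". Group A subjects then "receive the first cooling on the two thighs immediately after the end of the muscle soreness protocol", and group B starts cooling 24 hours later (section 2.3). Group C "will not receive any cooling intervention, nor any other intervention, for the entire period thereafter".

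On those who leave, section 4.2 says that their data are collected and stored, and that data already collected are analysed if consent is withdrawn. It adds: "Drop-outs are not replaced by the recruitment of new participants". It defines no analysis set and no method for missing values. The primary analysis is a repeated-measures ANOVA with four time points and three groups.

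**The concern.** A rule that ends participation because of a reaction to the treatment is a selection made after randomisation. Here only a cooled subject can meet it. If those who leave are also missing from the analysis, a cooled group without its cold-intolerant members is compared with a control group that still contains such people, unidentified.

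This matters most for soreness, which is self-rated on a VAS, while the symptom named in section 4.1 is severe pain or discomfort. If people who find cold painful also rate soreness higher, their loss lowers mean soreness in the cooled arms without any effect of cooling. Each subject is 1 of 15.

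The second hypothesis (immediate versus delayed cooling) may also be touched. By the cooling logs in section 2.3, group A has up to 4 x 3 = 12 sessions from day 1 and group B up to 3 x 3 = 9 from day 2, so the two arms do not have the same opportunity to meet the rule.

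**Working it through.** **1. What does the rule end?** The protocol mostly uses *examination* for trial participation: section 2.3 calls the examination a clinical trial, subjects are admitted to it (3.2) and excluded from it (3.4), and 4.2 speaks of patients who discontinue it. For a single application, section 4.1 says cooling session. Participation is therefore the more natural reading, but the text does not settle it.

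**2. Who can trigger it, and when?** Lots are drawn on the baseline day, before any cooling. Group C is never cooled. The trigger therefore arises after allocation and only in A and B. Cold allergy (Raynaud's syndrome) is screened in all arms before allocation and does not create the imbalance.

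**3. Does leaving mean leaving the comparison?** Section 4.2 does not say that visits continue after discontinuation. A standard repeated-measures ANOVA uses only subjects with all four measurements. A subject who leaves before 72 h would then be dropped, even though the earlier values are kept on file.

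**4. The plan's own figures.** Inputs from section 4.1: SD 2.1, differences 2.51 and 2.85 cm, 13 per arm, two-sided alpha 0.05. Exact t-test power is 0.8323 and 0.9129, matching the stated 0.83233 and 0.91287. Dropout: 13 / 0.9 = 14.4, rounded up to 15, so 2 losses per arm are allowed for, equally in all arms. The sample-size arithmetic is not in question.

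**5. Power.** With 15 controls and 13 left in the cooled arm, power is 0.859 (A) and 0.931 (B), against 0.885 and 0.948 with 15 in each. The loss is small; the issue is bias.

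**6. Size of the bias on the VAS.** Assumptions, not in the documents: no true cooling effect, normal values with SD 2.1, the k least cold-tolerant of 15 lost from one cooled arm, and correlation r between cold intolerance and soreness rating.

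Expected shift = r x k x m x SD / (15 - k), where m is the mean of the k highest of 15 standard normal values. For k = 2, m is about 1.49:

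- r = 1: 2 x 1.49 x 2.1 / 13 = 0.48 cm; 0.48 / 2.51 = 19%
- r = 0.7: 0.7 x 0.48 = 0.34 cm; 0.34 / 2.51 = 14%
- r = 0.3: 0.3 x 0.48 = 0.14 cm (0.146 by simulation); 0.146 / 2.51 = 6%
- r = 0: no shift

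Simulation (40,000 trials per setting, two-sample t-test at nominal 0.05) gives:

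| Lost of 15 | Shift towards cooling, r = 0.3 to 0.7 (cm) | Type I error |
|---|---|---|
| 1 | 0.08 to 0.18 | 0.053 to 0.060 |
| 2 | 0.15 to 0.34 | 0.054 to 0.076 |
| 3 | 0.20 to 0.48 | 0.059 to 0.095 |
| 4 | 0.26 to 0.63 | 0.062 to 0.124 |

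**The case against.** The strongest reply is that the plan nowhere says cold-intolerant subjects are left out of the analysis. The rule says discontinued, not excluded. The second sentence in section 4.1 may be a first step taken before intolerance is established, so the two need not contradict each other. Section 4.2 has discontinuers' data collected, which could mean that collection continues, and it analyses data already collected even after consent is withdrawn. This stands in part: intended exclusion cannot be inferred. But no sentence says that the 24, 48 and 72 h visits go on, and the named analysis has no place for incomplete subjects.

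Three stronger readings are tempting and are not supported.

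- *Section 3.4 is a second exclusion that acts by arm.* It reads: "Participants will be excluded from the examination if an imminent injury or illness contraindications exercise or cold application". It concerns injury or illness, covers exercise as well as cold, and is not worded by arm, so it can apply to a control.
- *All primary endpoints are biased.* The argument runs through pain rating. Nothing in the documents links cold tolerance to the blood markers, ultrasound thickness or maximal contraction. Bias there is possible but not shown.
- *The effect could be a quarter of the planned difference with two losses.* If the two lost would have rated 2 SD above average, the shift is 2 x 4.2 / 13 = 0.65 cm (26%). That exceeds the 0.48 cm expected even under perfect selection. A 1 SD excess (2 x 2.1 / 13 = 0.32 cm) already implies a correlation of about 1 / 1.49 = 0.67.

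It is also fair that section 5.2.1 rates the likely incidence of cooling pain as small, and that the plan's 2 losses per arm cover all causes. Few losses from intolerance may occur.

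**Conclusion.** The concern holds in a limited form and should be corrected. Section 4.1 leaves open what ends on cold intolerance. On the more natural reading, it is a stated rule that acts after randomisation in groups A and B only, and nothing in section 4.2 or in the named analysis prevents the loss of those subjects from the comparison.

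The dependence on arm follows from the documents; the size and direction of any bias do not. They rest on an assumed number of losses and an assumed link between cold intolerance and soreness rating. With 2 of 15 lost, a shift of about 0.15 to 0.34 cm on the VAS is a reasonable illustration, with type I error of 0.054 to 0.076 instead of 0.05. This is modest beside the planned 2.51 cm, but it would favour cooling and is avoidable.

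**What to change.** In sections 3.4, 4.1 and 4.2:

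- Separate stopping cooling from leaving the study. Whatever the cooling rule is, a participant whose cooling is stopped, or who cancels sessions, continues the scheduled 24, 48 and 72 h measurements, unless consent is withdrawn or a measurement is itself contraindicated under section 3.4. The exception is needed because each visit includes a maximal contraction test.
- State that all randomised subjects are analysed in the group allocated, with a method that keeps subjects with partial data, such as a mixed model with time, group and their interaction.
- Reconcile the two sentences at the end of section 4.1 so that it is clear what ends. The decision to stop cooling is left as it is.
- Report stopped cooling and departures by arm and reason.

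The cost is a few sentences and a different analysis procedure; the visits are already scheduled. The downside is small: the estimated effect will include people who stopped cooling and may be slightly smaller.
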